3.5. Determination of Sample Size

This study will enroll 24 subjects, 12 per arm. The sample size was determined based on practical considerations, as well as statistical considerations. Assuming standard deviation (SD)=9, with N=24 subjects (12 per arm), at a 2-sided 5% alpha-level, the study will have more than 80% power to detect an absolute between treatment difference of 11 percentage points in the primary endpoint (maximum percentage decrease in the FEV₁ measured 3 to 7 hours after allergen challenge).

[Table 1](#) presents the 95% confidence intervals (CIs) for observed differences between treatment in maximum percentage decrease in LAR FEV₁.

This document is confidential.

Table 1. CIs (95%) for Observed Differences Between Zavegeptant and Placebo in Maximum Percentage Decrease in LAR FEV₁

Observed Absolute Difference in Maximum % Decrease in LAR FEV ₁	2-sided 95% CI
9%	(1.4%, 16.6%)
11%	(3.4%, 18.6%)
13%	(5.4%, 20.6%)

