EAR	Early Asthmatic Response
ECG	Electrocardiogram
ELISA	Enzyme-Linked Immunosorbent Assay
FEV1	Forced Expiratory Volume in 1 Second
FVC	Forced Vital Capacity
GCP	Good Clinical Practice
ICH	International Conference on Harmonization
IP	Investigational Product
IRB	Institutional Review Board
IWRS	Interactive Web-based Response System
LAR	Late Asthmatic Response
MedDRA	Medical Dictionary for Regulatory Activities
mitT	Modified Intent-to-Treat

This document is confidential.

Abbreviation	Description
NCA	Non-compartmental Analysis
PK	Pharmacokinetic
PT	Preferred Term
REB	Research Ethics Board
SAE	Serious Adverse Event
SAP	Statistical Analysis Plan
SOC	System Organ Class
SOP	Standard Operating Procedure
S-STS	Sheehan Suicidality Tracking Scale
TFL	Table, Figure and Listing
WHO	World Health Organization

This document is confidential.

SAP text Version: SAP text version 2.0 24-May-2023

Filing requirements: TMF

Page 8 of 42

2. Purpose

The purpose of this statistical analysis plan (SAP) is to ensure that the data listings, summary tables and figures which will be produced, and the statistical methodologies which will be used, are complete and appropriate to allow valid conclusions regarding the study objectives. This SAP is based on BHV3500-204 Protocol Version 3.0 (22Mar2023).

The Rimegepant (BHV3000)/Zavegepant (BHV3500) Core Statistical Analysis Plan (the “Core SAP”) describes analysis details and methodologies common to the BHV3500 program and is incorporated by reference. The Core SAP assumes primacy for any matter where this SAP is silent (and the relevant content of the Core SAP could feasibly apply) or where the Core SAP is directly referenced as applicable. Otherwise, should any discrepancy exist between the Core SAP and this SAP, this SAP assumes primacy.

Note that the study was terminated prematurely in 1Q2023 due to low enrollment. Thus, the SAP is being amended from Version 1.1 to 2.0 to reduce the number of TLFs to streamline the CSR.

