3.2. Secondary Objectives

The secondary objectives of this study are:

- To evaluate the allergen-induced early asthmatic response (EAR) between subjects treated with zavegeptant and placebo.
- To evaluate the allergen-induced airway hyperresponsiveness (AHR) measured at 24 hours post-allergen challenge, between subjects treated with zavegeptant and placebo.
- To assess the safety and tolerability of oral zavegeptant.

This document is confidential.

SAP text Version: SAP text version 2.0 24-May-2023

Filing requirements: TMF

Page 10 of 42

[figure not shown]
Study Details/Design

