3.4. Brief Description

This is a multicenter, phase 1b, double-blind, parallel-group, randomized study of 24 subjects to evaluate the safety and efficacy of 150 mg oral zavegeptan versus placebo twice daily for the treatment of allergen-induced asthma. Individuals with stable, mild allergic asthma, with a history of episodic wheeze and shortness of breath, will be eligible for enrollment. The study will be divided into 2 parts. Part 1 is the screening period of up to 28 days to obtain a cohort of subjects with documented EAR (defined as $\geq 20\%$ fall in forced expiratory volume in 1 second (FEV₁) 0 to 2 hours after allergen challenge) and LAR (defined as $\geq 15\%$ fall in FEV₁ 3 to 7 hours after allergen challenge) to an inhaled incremental allergen challenge and AHR defined by methacholine PC₂₀ ≤ 16 mg/mL by inhaled incremental methacholine challenge. Part 1 consists of Visits 1 through 4. Part 2 is the dosing period of approximately 28 days. Part 2 consists of Visits 5 through 9. Subjects will be randomized in a 1:1 ratio to receive 150 mg zavegeptan or matching placebo to be taken twice daily. All subjects will undergo a 3-day allergen challenge triad, morning doses will be taken before any laboratory procedures and study treatment will end with their evening dose at the end of the challenge. A follow-up period consisting of an onsite visit will be conducted approximately 7 to 10 days after the last study treatment.

Figure 1 presents the general study schematic.

Figure 1. Study Schematic

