8.1. Primary Efficacy Endpoint and Analysis

8.1.1. Late Asthmatic Response

The primary efficacy endpoint is allergen-induced LAR, as assessed by maximum percentage decrease in FEV₁ between 3 and 7 hours post-allergen challenge at Visit 7, compared between zavegeptan and placebo using analysis of covariance (ANCOVA). The maximum percentage decrease is the difference between the baseline (pre-allergen challenge) FEV₁ at Visit 7 and lowest FEV₁ between hours 3 and 7 at Visit 7 divided by the baseline value from Visit 7. An ANCOVA model based on the decrease in FEV₁ between 3 and 7 hours post-allergen challenge with treatment as a factor and baseline LAR as a covariate will be fitted. The point estimate and 95% CIs will be reported for the difference in LARs comparing zavegeptan and placebo.

The LAR will also be assessed by an area under the curve (AUC) for the percent decrease in FEV₁ value between 3 to 7 hours. The AUC for percent decrease in FEV₁ will be compared between zavegeptan and placebo using ANCOVA. ANCOVA model based on the AUC for the percent decrease in FEV₁ between 3 and 7 hours at Visit 7 with treatment as a factor and baseline (pre-allergen challenge) FEV₁ at Visit 7 as a covariate to adjust for AUC will be fitted. AUC will be calculated using the trapezoidal method to estimate the areas over the observation time. The point estimate and 95% CIs will be reported for the difference in AUCs comparing zavegeptan and placebo.

Additional supportive endpoints, including minimum absolute FEV₁ value in 3 to 7 hours and AUC of the absolute FEV₁ values in 3 to 7 hours at Visit 7 will also be analyzed. The minimum absolute FEV₁ will be the lowest value between hours 3 and 7 post-allergen challenge at Visit 7 and AUC will be calculated as described above. Both endpoints will be compared between zavegeptan and placebo using an ANCOVA model with treatment as a factor and baseline FEV₁ at Visit 7 as a covariate. The baseline value is the measurement prior to dosing at Visit 7. The point estimate and 95% CIs will be reported for the difference in minimum absolute FEV₁ or AUC when comparing zavegeptan and placebo.

The time-response curve of allergen-induced percentage decrease in FEV₁ may be plotted for baseline (screening allergen challenge) and Visit 7.

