11.2. Analysis Periods

Analysis periods are defined as follows:

- Pre-treatment: measurement date/time on or before the study drug start date. This period is used to derive baseline values and to assess safety endpoints. Note that all measurements are pre-treatment for subjects in the enrolled analysis set with missing study drug start date. Note that AEs with imputed start date equal to the study drug start date are NOT part of this period.
 - Pre-treatment will include Visits 1 – 5 / Study Days -29 – 1
- On-treatment: measurement date/time after the study drug start date through the study drug last date + 7 days or ending at the follow-up visit, whichever is earliest. This period is used to assess safety endpoints on treatment. Note that AEs with imputed start date equal to the study drug start date are part of this period.

This document is confidential.

- On-treatment will include Visits 6 – 8 / Study Days 1 – 28
- Follow-up: measurement date after the study drug last date + 7 days or starting at the follow-up visit, whichever is earliest. This period is used to assess safety endpoints during follow-up.
 - Follow-up will include Visit 9 / Study Days 35 – 41

See [Section 11.1](#) for derived dates for determining analysis periods. If measurement time is missing, not collected, or not applicable for a parameter, then the measurement date is compared to the derived date.

This document is confidential.

12. Interim Analyses

No interim analyses are planned for this study.

This document is confidential.

SAP text Version: SAP text version 2.0 24-May-2023

Filing requirements: TMF

Page 36 of 42

13. Changes from Analysis Planned in Protocol

The Treated Population is defined in the study protocol. However, it has been renamed the Safety Population in the SAP.

One additional study populations were added that are not defined in the study protocol, the Follow-up population.

This document is confidential.

14. Quality Control

SAS programs are developed to produce output such as analysis data sets, summary tables, data listings, figures or statistical analyses. An overview of the development of programs is detailed in Syneos Health Developing Statistical Programs SOP (3907) .

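### Does SAP v2.0 mislead by keeping 24 subjects and more than 80% power after the study was stopped for low enrollment?

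*SAP*

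**What the plan says.** SAP Section 2 states: "Note that the study was terminated prematurely in 1Q2023 due to low enrollment". It gives the purpose of the new version in the next sentence: "the SAP is being amended from Version 1.1 to 2.0 to reduce the number of TLFs to streamline the CSR". The page footer dates that version: "SAP text Version: SAP text version 2.0 24-May-2023".

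The design and sample-size text is still written as a plan. Section 3.4 opens with "This is a multicenter, phase 1b, double-blind, parallel-group, randomized study of 24 subjects". Section 3.5 opens with "This study will enroll 24 subjects, 12 per arm", then says "the study will have more than 80% power to detect an absolute between treatment difference of 11 percentage points in the primary endpoint", assuming an SD of 9 and a two-sided 5% level. Its Table 1 gives 95% intervals for observed differences of 9, 11 and 13 points. The substance is the same as in Protocol Section 15.1.

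For the primary analysis, SAP Section 8.1.1 says: "The point estimate and 95% CIs will be reported for the difference in LARs comparing zavegeptan and placebo". Section 13, on departures from the protocol's analysis, has two entries. One is "The Treated Population is defined in the study protocol. However, it has been renamed the Safety Population in the SAP"; the other records an added Follow-up population. Neither concerns the number of subjects.

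**The concern.** Within one version of one document, Section 2 says recruitment has ended short, while Sections 3.4 and 3.5 say in the future tense that 24 subjects will be enrolled and that power will exceed 80%. Nothing marks the later text as the original plan, and nothing in it points back to Section 2. The version was adapted elsewhere to a shorter report: Section 9 drops the PK analysis and Section 10.7 drops the COVID-19 analysis. Leaving the sample-size text untouched therefore looks like an oversight.

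What would be at stake is interpretation. If the treatment difference came out with an interval that includes zero, a reader who took the planned power at face value could treat it as good evidence against an 11-point effect. With a much smaller sample it would be weak evidence.

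**Working it through.** **Inputs (SAP 3.5):** difference 11 points, SD 9, 12 per arm, two-sided 5%.

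**The plan's own figures.** The standard error of the difference is 9 × √(1/12 + 1/12) = 3.674. The noncentrality is 11 / 3.674 = 2.994. The two-sample t test with 22 df then has 81.6% power (81.4% with 21 df, allowing for one covariate; 84.9% by the normal approximation). All exceed 80%.

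The 95% half-width is t(0.975, 22) × 3.674 = 2.074 × 3.674 = 7.62. Around 9, 11 and 13 this gives (1.4, 16.6), (3.4, 18.6) and (5.4, 20.6), which matches Table 1 exactly. The section is arithmetically correct for the design it describes.

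**What a shortfall would do.** The documents give no achieved number, so the rows below 12/12 are assumptions. Same formulas, SD 9, df = n1 + n2 − 2:

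| Per arm | Power for 11 points | 95% half-width |
|---|---|---|
| 12/12 | 81.6% | 7.62 |
| 12/11 | 79.7% | 7.81 |
| 11/11 | 77.8% | 8.01 |
| 10/10 | 73.4% | 8.46 |
| 8/8 | 62.4% | 9.65 |
| 6/6 | 48.1% | 11.58 |
| 4/4 | 30.8% | 15.57 |

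The result also depends on whether SD 9 is before or after adjustment for baseline, which the documents do not say. If it is before, the residual SD is 9 × √(1 − ρ²). At 10/10, power is 77.0% for an assumed ρ of 0.3 and 84.5% for 0.5. So no single replacement figure can be derived.

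**Does any result use these figures?**

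- Section 2 comes before 3.4 and 3.5 and discloses the termination and its cause.
- Section 3.5 explains how the size was chosen. Its power statement is conditional on an SD of 9 and 24 subjects, and stays true as a conditional statement.
- Section 7.1 tabulates the number in each analysis set, 7.2 enrollment by country and site, and 7.3 disposition.
- Section 8.1.1 reports an estimate and interval computed from the subjects observed. It has no p-value and no success rule that refers to the planned size.
- Section 13 concerns changes of analysis. A recruitment shortfall is an outcome of trial conduct, and the primary model and analysis set do not depend on it.

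**The case for a change.** The best case for a change is that the margin is thin and the label costs almost nothing. By the t calculation the loss of a single subject takes power from 81.6% to 79.7%. The mITT set also needs a post-baseline LAR value, so the number analysed can fall below the number randomised. Protocol Section 15 says the SAP prevails where the two differ, so the SAP's statement of size is the controlling one. Because 8.1.1 drops the p-value that Protocol 15.2.1 promised, Section 3.5 is the only stated benchmark for precision.

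The facts in this stand: the text is dated, it is unlabelled, and a shortfall is the natural reading of Section 2. The inference to a needed change does not. The benchmark for a reported result is its own interval, which widens with the loss of subjects whatever Section 3.5 says. Power recalculated at the achieved size would add nothing to that interval.

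It is also tempting to name a size below which the trial stops being informative. With SD 9 the half-width first exceeds 11 points at 7/6 (11.02), a total of 13. That threshold does not mark where harm begins, because it applies only to an interval centred exactly on 0 or on 11. At the planned 12/12, any estimate between 11 − 7.62 = 3.38 and 7.62 already gives an interval containing both values; 5.5 gives (−2.1, 13.1). Always separating them would need a half-width of at most 5.5, which the planned design never had.

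**Conclusion.** No change is needed. The wording is a planning rationale carried forward into a late amendment with a narrow stated purpose. It is correct for the planned design, and the termination is disclosed ahead of it in the same document. Following the SAP as written gives the same estimates, intervals, analysis sets and tables whether or not 3.4 and 3.5 are labelled as history, so the effect on results is nil.

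The remaining risk is a misreading of planned power by someone who skips both Section 2 and the reported interval. The possible loss of power is real, but it comes from recruitment and no SAP wording can restore it. Its size is unknown: the range from 79.7% at 12/11 to 30.8% at 4/4 rests on assumed sample sizes and on SD 9 applying without covariate gain. A short note calling 3.4 and 3.5 the original planning basis would be a courtesy to the reader, with no statistical gain.

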3.6. Treatment Assignment and Blinding

The investigator or designee will obtain a subject number and treatment assigned via an Interactive Web-based Response System (IWRS). The IWRS system will assign a subject specific blinded study treatment kit that will contain 8 wallets, enough for the total treatment duration, to be dispensed to subjects. Once the kits/wallets have been assigned, they cannot be dispensed to another study subject.

Once a subject completes the study, or if a subject is discontinued early from the study, the investigator or designee must access the IWRS to document discontinuation of the subject from study participation.

After the subject's treatment assignment number is obtained from the IWRS, the number will be provided to the investigator or designee at the study center who is responsible for distribution of study treatment. The IP and placebo will be identical in appearance and labeled in a blinded manner. No study site personnel, subject, Sponsor personnel, or Sponsor designee will be unblinded to treatment assignment throughout the duration of the study unless unblinding is required. If an investigator becomes unblinded to a given subject's study treatment, that subject will be discontinued from the study unless there are ethical reasons for the subject not to be discontinued; approval from the Sponsor's medical monitor must be obtained in such instances.

In the event that an emergency unblinding is required for a subject because of an adverse event (AE) or concerns for the subject's safety or well being, the investigator may break the randomization code for the subject via the IWRS. The investigator is responsible for notifying the medical monitor and/or Sponsor of such an event as soon as possible. The unblinding and its cause will also be documented in the electronic case report form (eCRF).

3.7. Administration of Study Medication

After subjects have met all eligibility requirements in Part 1 and completed the rest/washout period, they will be randomized in a 1:1 ratio to receive zavegeptant or placebo. IP will be dispensed at Visit 5. Subjects will take 6 25-mg capsules twice daily, in the morning and evening, for at least 28 days. Subjects should dose consistently at the same time of day, preferably in the morning and evening. Each dose of study drug should be taken while fasting (e.g., at least 1 hour before breakfast/first meal of the day for the first dose, and at least 4 hours after the previous meal for the second dose). Subjects should not consume food other than water for 1 hour after dosing.

This document is confidential.

3.8. Study Procedures and Flowchart

The schedule of assessments is provided in [Table 2](#) as below.

This document is confidential.

SAP text Version: SAP text version 2.0 24-May-2023

Filing requirements: TMF

Page 13 of 42

Table 2. Schedule of Assessments

Visit #	Part 1: Screening ^a				2-4 Week Washout From Screening	Part 2: Dosing/Treatment				Follow-up
	1	2	3	4		5	6	7	8	
	3-Day Allergen Triad					3-Day Allergen Triad				
Day(s)	-29 to -16	-15 (±3d)	-14 (±3d)	-13 (±3d)		1 ^b	~26 (+3d)	~27 (+3d)	~28 (+3d)	~35 - 41
Informed consent	X									
Inclusion/Exclusion criteria	X	X	X			X				
Demographics/ Medical history/medication history	X									
Vital signs	X					X	X	X	X	
Physical examination, including BMI ^c	X									X
Electrocardiogram	X									X
Spirometry	X	X	X	X		X	X	X	X	
Pregnancy test ^d	X					X			X	
Clinical laboratory tests (hematology, chemistry)	X					X				X X
Urinalysis	X					X			X	
Urine drug testing	X									
Allergy skin (prick) test	X									
Methacholine challenge		X		X		X	X		X	
Sputum induction		X	X	X		X	X	X	X	
Allergen skin titration test ^e	X	X								
Allergen inhalation challenge			X					X		
Randomization and Dosing ^{f,g}						X	X	X	X	
Meal and Daily Study Drug Dosing Diary ^h						X	X	X	X	
Pharmacokinetic							X	X	X	

This document is confidential.

Visit #	Part 1: Screening ^a				2-4 Week Washout From Screening	Part 2: Dosing/Treatment				Follow-up
	1	2	3	4		5	6	7	8	
	3-Day Allergen Triad					3-Day Allergen Triad				
Day(s)	-29 to -16	-15 (± 3 d)	-14 (± 3 d)	-13 (± 3 d)		1 ^b	~26 (+ 3d)	~27 (+ 3d)	~28 (+ 3d)	~35 - 41
sampling ⁱ										
Ongoing and concomitant medications	X	X	X	X		X	X	X	X	X
Adverse events		X	X	X		X	X	X	X	X
S-STS	X					X			X	

Abbreviations: BMI=body mass index; d=day; ECG=electrocardiogram; FEV₁= forced expiratory volume in 1 second; h=hour(s); max=maximum; min=minimum; PC₂₀=provocation concentration causing a 20% decline in FEV₁; SABA= short-acting beta-agonists; S-STS=Sheehan-Suicidality Rating Scale; WOCBP=women of childbearing potential.

a Part 1: All screening procedures will be completed and results returned within Days -29 to Day -13.

b Part 2/Day 1: Subjects will be confirmed as recovered on Day 1 (e.g., confirmation of hyperresponsiveness recovery of methacholine PC₂₀ not more than 1 doubling dose lower than baseline; return to FEV₁ within 90% of baseline) prior to initiation of dosing.

c A full examination will be performed at screening and at follow-up. BMI will be calculated at Screening Visit 1.

d Serum pregnancy test conducted at screening; urine pregnancy testing at all other visits as indicated. Results of the pregnancy test are required before dosing. Source documents should document that WOCBP agree to use 2 effective forms of contraception and men with WOCBP partners agree to use condoms with a spermicide during treatment.

e Allergen skin titration test can be performed at either Visit 1 or Visit 2 to allow for flexibility.

f After randomization, daily dosing in Part 2 from Visit 5 through Visit 8, inclusive. No onsite visit required after start of study medication at Visit 5 to start of allergen triad (Visit 6). Every effort should be made to conduct the study visits within the specified windows in Part 2. However, if necessary due to local COVID-19 safety requirements, visits may be performed outside of these windows in order to minimize any potential risks to subject safety and to comply with governmental and institutional guidance.

g Subjects should dose consistently at the same time of day, preferably in the morning and evening. Each dose of study drug should be taken while fasting (e.g., at least 1 h before breakfast/first meal of the day for the first dose, and at least 4 h after the previous meal for the second dose). Subjects should not consume food other than water for 1 h after dosing.

h Subjects will be asked to complete a daily diary to capture date and times of both meals and study drug administration.

i Pharmacokinetic sampling to be conducted predose on Visits 6, 7, and 8, and additionally at Visit 7 at approximately 1 (+ 0.5 h) h and 3 (+/- 0.5 h) h postdose. Subjects should be instructed to hold their daily dose of study drug on the morning of Visits 6, 7, and 8 and arrive at the clinic after an overnight fast. Exact times of dosing and PK sample collection will be documented.

This document is confidential.

4. Estimands

An estimand is the target of estimation to address the scientific question of interest posed by a study objective. The four attributes of an estimand include the population of interest, endpoint of interest, summary of the endpoint, and specification of how intercurrent events are reflected in the scientific question of interest.

For all objectives, the population of interest is defined through appropriate inclusion/exclusion criteria to reflect the targeted patient population for approval.

Intercurrent Events

Intercurrent events are those that occur after treatment initiation and either preclude observation of the endpoint or affect its interpretation.

- For efficacy objectives, study drug discontinuation is handled with a “treatment policy strategy”, i.e., the occurrence of the intercurrent event is considered irrelevant, such that all observed values of the endpoint of interest are used regardless of study drug discontinuation. This strategy aligns with the assumption that zavegepant is expected to confer benefits to the subject after study drug discontinuation. Thus, premature study drug discontinuation is ignored for these efficacy endpoints.

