8.6 Study Withdrawal, Removal, and Replacement of Subjects

Although the importance of completing the entire clinical study will be explained to the subjects, any subject is free to withdraw consent from the study at any time and for whatever reason, without any prejudice. The Sponsor and the investigator or designee may discontinue study drug or withdraw any participant from the study for reasons described below:

- subject request (consent withdrawal);
- safety reasons;
- non-compliance with study drug or protocol requirements;
- significant protocol deviation;
- positive pregnancy test.

If a subject discontinues study treatment and is withdrawn from the study for any reason, the study site must immediately notify the medical monitor. The date and the reason for study discontinuation must be recorded on the electronic case report form (eCRF). Subjects who complete or discontinue early from the study will be asked to complete the Visit 9 follow-up within 7 to 10 days of the last administration of study drug to complete assessments as indicated in the Schedule of Assessments ([Table 10-1](#)).

In the event that a subject discontinues prematurely from the study because of a TEAE or serious TEAE, the TEAE or serious TEAE will be followed up until it resolves (returns to normal or baseline values) or stabilizes, or until it is judged by the investigator and medical monitor to no longer be clinically significant.

Once a subject is withdrawn from the study, the subject may not reenter the study.

Participants who withdraw or are withdrawn from the study after dosing may be replaced at Sponsor's discretion.

As soon as participant withdrawal is confirmed, sampling and scheduling will be stopped. Study exit procedures will be performed at the time of withdrawal from the study or as soon as possible thereafter.

Additionally, the Sponsor may stop the study at any time for safety, regulatory, legal, or other reasons aligned with Good Clinical Practice (GCP). This study may be terminated at the discretion of the Sponsor or any regulatory agency. An investigator may choose to discontinue or stop the study at his or her study site for any reason, including safety or low enrollment.

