4.1. Primary Endpoint

Table 1: Primary Objective Estimand

Objective	To evaluate the allergen-induced LAR 3 to 7 hours after the administration of the allergen inhalation challenge between subjects treated with zavegepant and placebo.
Efficacy Endpoint	Maximum percentage decrease from baseline in FEV ₁ at any time between 3 and 7 hours post-allergen challenge in the modified intent-to-treat (mITT) analysis set.
Summary	Difference in maximum percentage decrease from baseline in FEV ₁ between the zavegepant and placebo groups using an ANCOVA model.
Intercurrent Events	Treatment policy strategy : All available assessments on the subject are used regardless of intercurrent events.

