5.1. Analysis Sets

Enrolled: The enrolled analysis set includes all subjects who sign the informed consent form (ICF) and are assigned a subject identification number by the IWRS.

Full: The full analysis set includes enrolled subjects who receive a randomization treatment assignment from the IWRS.

Safety: The safety analysis set includes subjects from the full analysis set who received at least 1 dose of study therapy. The safety analysis set will be used for all analyses of safety endpoints. Subjects will be analyzed according to the treatment actually received.

Modified Intent-to-Treat (mITT): The mITT analysis set includes safety subjects (received at least 1 dose of study therapy) that provided at least 1 non-missing post-baseline LAR assessment. Subjects will be analyzed according to randomized treatment assignment.

Follow-up: Safety subjects whose last contact date is in the follow-up analysis period. This analysis set is used to assess follow-up safety.

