Incorrect study drug at least once means subject is (1) randomized to placebo group but received >=1 dose of study drug from study drug kit/container or (2) randomized to study drug group but received >=1 dose of study drug from placebo kit/container.

Incorrect study drug all the time means subject received incorrect study drug at least once (as defined above) and never received any randomized study drug.

A by-subject listing of study drug accountability is provided for the safety analysis set. Additionally, a by-subject listing of study drug accountability for partial/missed doses is provided for the safety analysis set.

An administrative listing of IP batch numbers is provided for the safety analysis set. Refer to the Core SAP for listing contents.

This document is confidential.

8. Efficacy

Efficacy will be measured via spirometry and lung function assessments. These assessments will be performed after each study dose treatment at Visit 5, Visit 6, Visit 7, and Visit 8. Methacholine PC₂₀ and airway inflammation will be assessed before and after study dose treatment, and allergen-induced methacholine PC₂₀, allergen-induced bronchoconstriction, and allergen-induced airway inflammation will be assessed following allergen challenges. All efficacy assessments will be performed on the mITT analysis set.

The methacholine inhalation test will be performed at Visit 2, Visit 4, Visit 5, Visit 6, and Visit 8. This test will measure FEV₁ at 30 and 90 seconds after each inhalation and, if necessary, at 180 and 300 seconds and beyond until the lowest response is captured. The test is terminated when a fall in FEV₁ of at least 20% (lowest post diluent FEV₁ versus lowest post methacholine concentration FEV₁) occurs, and the methacholine PC₂₀ is calculated. The PC₂₀ assessment will be performed at the start of each treatment period, then 24 hours before and 24 hours following allergen challenge as a measure of AHR.

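### Does the primary LAR estimand fail because dosed subjects with no Visit 7 allergen challenge fall outside the mITT set?

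*SAP*

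**What the plan says.** SAP Section 4 describes the target population for every objective: "the population of interest is defined through appropriate inclusion/exclusion criteria to reflect the targeted patient population for approval". It then defines the events that can complicate the estimate: "Intercurrent events are those that occur after treatment initiation and either preclude observation of the endpoint or affect its interpretation". For efficacy it names study drug discontinuation, handles it by treatment policy on observed values, and comments: "This strategy aligns with the assumption that zavegepant is expected to confer benefits to the subject after study drug discontinuation".

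The primary estimand table in SAP 4.1 has no population row. It locates the endpoint "post-allergen challenge in the modified intent-to-treat (mITT) analysis set" and applies treatment policy: "All available assessments on the subject are used regardless of intercurrent events". SAP Section 8 repeats the set: "All efficacy assessments will be performed on the mITT analysis set".

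Under SAP 5.1, mITT membership requires at least one dose and that the subject "provided at least 1 non-missing post-baseline LAR assessment". SAP 6.3 bases analyses on observed data. Protocol 8.6 adds: "As soon as participant withdrawal is confirmed, sampling and scheduling will be stopped".

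SAP Section 2 incorporates a Core SAP, which governs where this SAP is silent. It was not available for this review.

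**The concern.** Having a post-baseline LAR is something that happens after randomisation; it is not an eligibility criterion. A subject can meet every criterion, take study drug, withdraw before the challenge at about Day 27, and so belong to the population in SAP Section 4 but not to the primary analysis. The SAP's own definition of intercurrent events includes those that prevent the endpoint from being observed. Treatment policy on available assessments supplies no value for such a subject.

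The one assumption that the SAP does state, benefit persisting after the drug is stopped, does not fill the hole. Treatment policy does not need it, and it says nothing about a subject with no Visit 7 measurement.

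If unchallenged zavegepant subjects would have done worse than those challenged, mITT would overstate the effect in the eligible population, and no planned analysis in these two documents would show by how much.

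**Working it through.** **Can it happen?** Yes. The schedules of assessments place allergen challenges at Visits 3 and 7 only. One sentence in SAP Section 8 also mentions Visit 8, but the schedule and the opening sentence of the same paragraph do not, so it reads as a slip. Visit 9 has no spirometry or challenge. A dosed subject who misses Visit 7 therefore has no post-baseline LAR.

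**The plan's own figures first.** Inputs from Protocol 15.1 and SAP 3.5: SD 9, 12 per arm, difference 11 points, two-sided 5%.

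- Half-width = t(0.975, 22) × 9 × √(2/12) = 2.074 × 3.674 = 7.62. This reproduces the tabulated intervals (1.4, 16.6), (3.4, 18.6) and (5.4, 20.6).
- Power from the noncentral t distribution with 22 df is 81.6%, consistent with the stated more than 80%.

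**Size of the gap.** Assumptions: the effect among challenged subjects is 11; k of 12 zavegepant subjects are unchallenged; their mean fall in FEV1 would have been D points worse than that of challenged zavegepant subjects.

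Effect in all dosed subjects = 11 − (k/12) × D

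| Unchallenged subjects would have had | k = 1 | k = 2 | k = 3 |
|---|---|---|---|
| full benefit (D = 0) | 11.0 | 11.0 | 11.0 |
| half benefit (D = 5.5) | 10.5 | 10.1 | 9.6 |
| no benefit (D = 11) | 10.1 | 9.2 | 8.3 |

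Over D = 5 to 18 and k = 1 to 3 the result runs from 10.6 down to 6.5. Protocol 8.6 lets the sponsor replace dosed withdrawals. With full replacement (12 challenged, 12 + k dosed) the no-benefit gap is 11 × k/(12 + k) = 0.8, 1.6 and 2.2, against 0.9, 1.8 and 2.8 without it.

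**Against the precision of the estimate.** Simulated mITT ANCOVA (Visit 3 to Visit 7 LAR correlation 0.5, an assumption) gives 95% half-widths of 6.89, 7.05 and 7.32 for k = 1, 2, 3. The largest no-benefit gap, 2.75, is 2.75/7.32 = 38% of the half-width.

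**When mITT is unbiased.** It is enough that loss depends only on arm and Visit 3 LAR and that the effect is constant. Losing the k highest Visit 3 values with a constant effect gave 11.04, 10.97 and 10.96 against a true 11. These conditions are not necessary:

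- Random loss of three zavegepant subjects, with individual effects of 0 or 22 at random, gave 10.98 (simulation SE 0.04).
- Loss in each arm of the three subjects with the highest untreated Visit 7 LAR, with a constant effect, gave 11.03 (SE 0.03).

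**What a sensitivity model would add.** Imputing missing zavegepant values from the placebo regression on Visit 3 LAR has expected result 11 × (12 − k)/12, the bottom row of the table. Its simulated half-widths are 7.34, 7.81 and 8.33, so the full interval widens by 2 × 0.45 = 0.9, 2 × 0.76 = 1.5 and 2 × 1.01 = 2.0 points. If the missing subjects would have had full benefit, it is too low by 0.9, 1.8 and 2.8. In smaller samples with one zavegepant subject missing it deteriorates:

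| Per arm | mITT half-width | Imputed half-width |
|---|---|---|
| 10 | 7.70 | 8.38 |
| 8 | 8.99 | 10.16 |
| 6 | 11.24 | 14.10 |
| 5 | 13.34 | 22.79 |
| 4 | 17.51 | 179.9 |

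**What the reader will already have.** SAP 7.1 tabulates each analysis set, by arm under SAP 6.1, and lists membership by subject. SAP 7.3 lists reasons for non-completion, with free text and adverse event terms. SAP 7.4 lists significant deviations with visit, type and description. The safety and mITT counts give k, and the formula above then gives the gap for any D.

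**The case for a change.** The strongest case for a change is that an estimand section exists to prevent this kind of silence. SAP Section 4 lists population as an attribute of an estimand, and the table then omits it. An observed-data rule is a procedure, not an assumption. Withdrawal may be related to treatment, since Protocol 8.6 includes safety and non-compliance among the reasons. No onsite visit is required between Visit 5 and Visit 6, so there are weeks in which subjects can be lost. Equal numbers lost in both arms would not remove the gap if the lost zavegepant subjects had no benefit. Each lost subject also weighs more in a study that ended early.

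The factual part of this stands: neither document supplied states the assumption, and the persisting-benefit sentence does not provide it. Whether the Core SAP does cannot be checked here.

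The step from that to a defect does not stand. The two statements do different jobs: one names the patients about whom the study is asking, the other the subjects with data to answer. SAP Section 4 ties treatment policy to drug discontinuation and to observed values. It therefore covers the subject who stops the drug but is still challenged, and claims nothing for one who is not. Appendix A does pool missed challenges in one category. Even so, given the by-subject listings, the main case that could escape is a missed challenge not graded major in a subject who otherwise completes the study.

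**Conclusion.** No change is needed. The missing sentence is one that analysts supply as a matter of course: the mITT ANCOVA is read as an observed-data estimate, valid for the eligible population if unchallenged subjects are comparable given arm and screening LAR. Writing it down would alter no estimate, interval or table.

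The possible overstatement is 0.9 to 2.8 points if one to three of 12 zavegepant subjects were unchallenged and had no benefit at all. It is zero if they had full benefit, and in the extreme case shown (k = 3, D = 18) it is 4.5 points. All of these lie inside the mITT half-width of about 7. They rest on an assumed 11-point effect, SD 9, correlation 0.5 and an assumed number of losses; the documents give neither a withdrawal rate nor the final sample size.

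A placebo-based imputation is a fair option that statisticians would debate. It is a conservative bound only under a further untestable assumption, namely that the missing subjects would have done no worse than comparable placebo subjects. Its expected result follows from counts already planned for reporting. It also becomes unstable at the small sizes possible in a study stopped for low enrolment, whose SAP was amended to reduce outputs. Omitting it is a reasonable trade-off.
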